7.1.4. Generalizability

All patients will be required to have a total of 12 months of pre-index medical and prescription data. This may result in a study population that is less healthy with a higher incidence of fracture compared with that reported in ACTIVE. Regardless, this selection bias is not likely to differentially affect the 2 treatment cohorts. Results of the study are expected to be generalizable to the population of managed care enrollees including commercial and Medicare Advantage members. Regardless of this limitation, the data are representative of a broad population of patients from multiple payers and are geographically diverse across the USA. The study will provide additional information on real-world use and outcomes in patients new to treatment with ABL outside of the clinical study setting.

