Secondary Objective: 
 To evaluate the cardiovascular safety of ABL for the treatment of osteoporosis in postmenopausal women in the real-world healthcare setting in the USA compared with TPTD using the same cohort of PS-matched patients. 	Secondary Endpoints: 
 Time to the first incidence of the composite endpoint of nonfatal MI, nonfatal stroke, or in-hospital cardiovascular death within the 18 months after treatment initiation and while still on therapy. Time to the first incidence of the composite endpoint of nonfatal MI, nonfatal stroke, heart failure or in-hospital cardiovascular death within the 18 months after treatment initiation and while still on therapy.
Exploratory Objective: 
 To further evaluate the effectiveness and cardiovascular safety of ABL for the treatment of osteoporosis in postmenopausal women in the real-world healthcare setting in the USA compared with TPTD using the same cohort of PS-matched patients. 	Exploratory Endpoints: 
Efficacy
 
 Time to the first incidence of hip fracture within the 18 months after treatment initiation. 
Safety
 
 Time to the first incidence of MI Time to the first incidence of stroke Time to the first incidence of -in-hospital cardiovascular death Time to the first incidence of heart failure
Study Design: This is a retrospective observational cohort study using healthcare administrative claims data from the USA.	

Setting:

This study will use anonymized patient level data from PRA's Symphony Health Patient Source Integrated Dataverse (IDV) database. Data are routinely collected in healthcare encounters from all available healthcare sites (inpatient hospital, outpatient hospital, physician office, pharmacy, etc.) for all types of provided services including specialty, preventive care, and office-based treatments.

Study Population:

Patient Population:

The patients for inclusion in the study analyses will be identified based on the prescribed anabolic therapy filled (ABL or TPTD). The study intake period was chosen to coincide with the date of the FDA approval of ABL in the USA.

Data Sources:

This study will use anonymized patient claims data from the Symphony Health Patient Source IDV database including the enhanced hospital data.

Study Size:

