7. RESEARCH METHODS

7.1. Study Design

This will be a retrospective observational study using administrative data for the period from May 2012 to January 2021. The most recently available data at the time of data extraction will be used. This study will use anonymized patient claims data from PRA's Symphony Health Patient Source Integrated Dataverse (IDV) database with the inclusion of enhanced hospital data, which are claims and remittance from the inpatient hospital setting and proprietary Patient Transactional Dataset (PTD) claims and prescription data, to apply the inclusion/exclusion criteria for patient selection (see [Section 7.4.1](#)) to form the data set.

Figure 1 Study Design Schematic

ABL= abaloparatide; TPTD = teriparatide.

The **Identification Period** is the period of time during which subjects will be identified based on their index date (01 May 2017 to 30 June 2019).

The **Index Date** is the date on which the subject filed their first claim for a prescription for either ABL or TPTD during the identification period.

The **Pre-index Period** consists of the 5 years before the Index Date during which medical history was available for the subject.

The **Post-index Treatment Period** consists of the 18 months plus 30 days follow-up after the initiation of treatment with anabolic drug (ABL or TPTD) on the index date and continuing for the duration of treatment.

Treatment Cohorts

This is a real-world observational study. Treatments will not be assigned. Instead, cohorts are defined as follows:

- **Abaloparatide Cohort:** Patients who filled ≥ 1 prescription for ABL (TYMLOS) as their index medication during the identification period.

- **Teriparatide Cohort:** Patients who filled ≥ 1 prescription for TPTD (Forteo) as their index medication during the identification period.

Evaluation Period

The date of the first claim for either ABL or TPTD during the identification period (between May 1, 2017 and June 30, 2019) will be considered the index date.

- The medication received on the index date will be considered the index medication.
- Treatment duration may continue for up to 18 months (540 days) after the index date.
- The evaluation of outcomes will start immediately after treatment initiation and will continue for 18 months after the index date for both effectiveness and cardiovascular safety evaluation regardless of the drug possession gap between any 2 prescription fills.

Primary Analyses

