7.4. Study Population

7.4.1. Subject Selection Criteria

Table 1 details the inclusion criteria and Table 2 provides the exclusion criteria for this study.

Table 1 Inclusion Criteria

Criterion	Details	Order of Application	Assessment Window	Code Type	Diagnosis Position	Applied to Study Populations	Varied for Sensitivity	Source for Algorithm
Women	Sex female	Before selection of the index date	Any time	NA	NA	Yes	No	NA
Age: \geq 50 years	\geq 50 years of age	Before selection of the index date	[0, 0]	NA	NA	Yes	No	Proxy for postmenopausal
\geq 1 prescription fill for ABL or TPTD	between May 1, 2017 and June 30, 2019 (identification period)	Will determine the index date	May 1, 2017 and June 30, 2019	NDC	NA	Yes	Yes. Further restriction on various duration of treatment	NA
\geq 1 claim for medical or hospital visit and a pharmacy claim	in the 12 months before the index date	Before selection of the index date	0-12 months pre-index	NDC, ICD, HCPCS	Any	Yes	Yes	PRA proprietary algorithm to determine coverage

ABL = abaloparatide; NA= not applicable; NDC = National Drug Code; post-index = after the index date; pre-index = before the index treatment date; TPTD = teriparatide.

Table 2 Exclusion Criteria

Criterion	Details	Assessment Window	Code Type	Diagnosis Position	Applied to Study Populations	Varied for Sensitivity	Source for Algorithm
Paget's disease	Presence of ≥ 1 claim for Paget's disease	Pre-index	ICD	Any	Yes	No	NA
Malignancy	Presence of ≥ 1 claim except for nonmelanoma skin cancers, carcinoma in-situ of the cervix, ductal carcinoma in-situ of breast	Pre-index	ICD	Any	Yes	No	NA
Indicators of high disease burden and high risk of death	CCI > 10	Pre-index	ICD	Any	Yes	No	NA
With prior index anabolic treatment	Anabolic treatment includes ABL, TPTD and romosozumab	Pre-index	NDC and HCPCS	NA	Yes	No	NA
Switch to a different anabolic treatment after index	Anabolic treatment includes ABL, TPTD and romosozumab	Index-date to 18 months after	NDC and HCPCS	NA	Yes	No	NA

CCI = Charlson Comorbidity Index; ICD = International Classification of Diseases; NA= not applicable; pre-index = before the index treatment date; post-index = after the index date.

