7.5. Data Sources

This study will use anonymized patient level data from PRA's Symphony Health IDV database, including the enhanced hospital data. PRA's IDV database is a large nationally representative claims-based database. The database cross-sectionally covers over 80% of the population in the USA (approximately 300 million lives) annually. It includes claims submitted to all payer types, including commercial plans, Medicare, and Medicaid. In terms of the pharmacy claims, it captures approximately 92% of the retail and 65% specialty pharmacy claims, and approximately 68% of mail order claims. For medical claims, it covers approximately 60% of professional claims in an outpatient setting. Medical claims are open unadjudicated claims. Mortality data recorded on the hospital (medical facility) discharge status covers about 1/3 of the total death records. According to National Center for Health Statistics data published on CDC wonder (CDC, 2021), 35% total deaths in 2019 happened at medical facility which includes hospital inpatient, outpatient or emergency room, death on arrival or unknown status. This number is slightly high (37%) for cardiovascular death (cause of death is I00 to I99 in ICD-10). For women at age 50, 54% percentage of cardiovascular death occurred in medical facilities. The data are de-identified, in compliance with Health Insurance Portability and Accountability Act (HIPAA) guidelines, with stable unique identifiers to allow for longitudinal tracking over time. The terms of the Research Exception provisions of the Privacy Rule, 45 Code of Federal Regulations (CFR) Part 164.514(e) exempts Institutional Review Board (IRB) approval for this nonexperimental study, which is fully HIPAA compliant.

Table 3 summarizes the calendar time range used to ascertain cohort entry (index date), as well as the calendar time range of data available for pre-index- assessment windows and post-index follow up (study period). The data source name and version are identified, as well as any sampling criteria applied (for example, the data cut only includes patients with a diagnosis of diabetes). If data linkage is involved, provide a citation or an appendix with description of the linkage (how, performance characteristics).

All individual data will be de-identified and signed data license agreements will be in place for all data sources.

Table 3 Metadata About Data Source and Software

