7.6.2. Risk Factors

Conditions associated with increased risk of fractures or falls ([Camacho et al, 2020](#)), including pre-index fracture history, for which data are available in administrative claims, will be assessed by the presence of ICD codes in the claims database. History of co-morbidities associated with an increased risk of falls and/or fractures, as well as those conditions associated with poor bone health, will be assessed (see [Section 7.6.3](#) for the list of co-morbidities).

Data for medical history associated with a high risk of cardiovascular events will also be extracted: MI, stroke, and heart failure.

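### Section 7.1.4 promises 12 months of pre-index data, but Table 1 as written needs only one medical and one pharmacy claim in that year, and the sensitivity analysis it signals is missing

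*Combined protocol and SAP*

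**What the plan says.** Section 7.1.4 sets the requirement in prose: "All patients will be required to have a total of 12 months of pre-index medical and prescription data". It adds that the resulting selection is unlikely to act differently on the two cohorts, and gives no data for this.

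Section 7.2 says that patients are selected by Tables 1 and 2. The matching row of Table 1 (section 7.4.1) asks for at least one "claim for medical or hospital visit and a pharmacy claim" in the 12 months before index. Its algorithm source is given as "PRA proprietary algorithm to determine coverage", with no description. Its *Varied for Sensitivity* entry is Yes.

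The history window is longer. The pre-index period in section 7.1 "consists of the 5 years before the Index Date during which medical history was available for the subject". Table 2 excludes patients "With prior index anabolic treatment" and patients with a malignancy claim, both over the pre-index period. Section 7.6.2 says that risk factors, including fracture history, "will be assessed by the presence of ICD codes in the claims database". Section 7.8.11.1 splits patients by bisphosphonate use within 5 years.

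On completeness, section 7.5 says that medical claims are open and unadjudicated, that about 60% of outpatient professional claims are covered, and for pharmacy that "it captures approximately 92% of the retail and 65% specialty pharmacy claims, and approximately 68% of mail order claims".

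**The concern.** One claim of each type shows that a woman was visible at some moment in the year, not that she was observable for the year. Read literally, Table 1 admits a woman who enters the database only a month before her index fill. For her, the absence of earlier anabolic fills, fractures, cancer codes or bisphosphonates carries little information, yet no rule in the plan separates no claim from not observed.

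Two claims of the study rest on that history: that patients are new to anabolic therapy, and that the arms are matched on fracture and treatment history. The balance criterion in section 7.8.5 (standardized difference below 0.10) sees recorded values only, so it cannot reveal imbalance in what was never recorded. If observability differs by arm, the primary hazard ratio, tested against a margin of 1.3, carries a bias that no planned output would display.

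**Working it through.** **1. The texts side by side**

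| Item | Where | Content |
|---|---|---|
| Stated requirement | 7.1.4 | 12 months of medical and prescription data |
| Operative criterion | Table 1 | at least one medical or hospital claim and a pharmacy claim in 12 months |
| Source of the criterion | Table 1 | proprietary coverage algorithm, undescribed |
| Minimum observable time in the 5 years | 7.1 | none stated |
| Sensitivity flag on this row | Table 1 | Yes |
| Matching analysis | 7.8.10.1, 7.8.10.2 | none |

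Section 7.8.10 lists calipers, exposure duration, prior denosumab or zoledronic acid, all-cause in-hospital death and new-incident cardiovascular events. The exposure-duration analyses answer the other Table 1 row flagged Yes (the prescription fill). Nothing answers this one.

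**2. Calendar look-back is adequate.** The study period opens on 1 May 2012 and intake on 1 May 2017: 1,826 days. Every index date has five calendar years of database behind it. The gap is in patient-level observability.

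**3. Illustration: hidden prior users.** The plan gives no figure here, so the inputs are assumptions. Let a share q of candidates truly have prior anabolic use, detected with probability s. The hidden share among apparent new users is h = q(1 − s)/(1 − qs). Take q from 5% to 30%, and s from 0.65 to 0.92, borrowing the specialty and retail capture rates of section 7.5 as proxies.

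- q = 5%, s = 0.92: 0.004/0.954 = 0.4%
- q = 10%, s = 0.92: 0.008/0.908 = 0.9%
- q = 10%, s = 0.65: 0.035/0.935 = 3.7%
- q = 30%, s = 0.65: 0.105/0.805 = 13.0%

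Suppose, as the extreme case, that hidden users sit only in the teriparatide arm, with fracture hazard r times that of new users. The hazard ratio is then multiplied by 1/(1 + h(r − 1)). The standard error of the log hazard ratio is √(4/560) = 0.0845, from 2 × 8,000 × 3.5% = 560 events. One-sided error at a true hazard ratio of 1.3 is Φ(−ln(multiplier)/0.0845 − 1.96); without bias it is 2.5%.

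| h | r | HR multiplier | Error at margin |
|---|---|---|---|
| 3.7% | 0.7 | 1.011 | 1.8% |
| 3.7% | 1.3 | 0.989 | 3.4% |
| 13.0% | 0.7 | 1.041 | 0.8% |
| 13.0% | 1.3 | 0.962 | 6.6% |

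The sign depends on r, which the documents do not give.

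**4. Illustration: fracture history.** Section 6.1 gives an 86% increase in risk after any fracture (relative risk 1.86). With equal recorded prevalence p after matching, sensitivities s_A (abaloparatide) and s_T (teriparatide), and perfect specificity, the multiplier is (1 + 0.86p/s_A)/(1 + 0.86p/s_T).

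- Equal sensitivity (0.65 in both arms): 1.00
- p = 30%, s_A = 0.92, s_T = 0.65: 1.280/1.397 = 0.917
- p = 30%, s_A = 0.65, s_T = 0.92: 1.397/1.280 = 1.091

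Bias of this kind needs unequal sensitivity, and nothing in the documents shows it.

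**The case against.** **The coverage algorithm may demand more than one claim of each type.** This stands in part. One claim of each is the written minimum, not proven practice. But a reader cannot tell what was applied, and the criterion cannot be reproduced until the algorithm is described.

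**A reader might infer that the error falls on the teriparatide arm alone.** "The study intake period was chosen to coincide with the date of the FDA approval of ABL in the USA", whereas teriparatide dates from 2002, so unseen earlier use of one's own index drug has had more time to arise with teriparatide. That is a reason to check, not a demonstration. Intake runs to 30 June 2019, so abaloparatide users with uncaptured fills from 2017 or 2018 can also appear as new later on, and unseen prior teriparatide use can enter either arm. For fracture, malignancy and bisphosphonate history no argument for unequal observation is available. Section 6.3 reports similar disease characteristics and comparable market access.

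**Capture rates apply to claims, not patients.** This stands. A hidden continuing user must have all earlier fills missed and her index fill caught. If misses were independent, three fills would all be missed with probability 0.35³ = 4.3%, which at q = 30% gives h of about 1.8%, not 13.0%. Clustering by pharmacy would change this, and the documents do not say through which channel these drugs are dispensed.

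**A reader might also infer that index-day claims satisfy the criterion**, because the window is written as 0-12 months. The row's own detail and the table footnote place the window before the index date, so this is loose shorthand.

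**Coding unobserved history as absent is an inference** from code-presence definitions. The plan states no imputation rule, and the contents of Appendices 1, 3, 4 and 5 are not visible.

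**Conclusion.** The mismatch between section 7.1.4 and Table 1, and the missing sensitivity analysis, are established from the text and need no assumption. It follows that, applied as written, the criterion can admit women with little observable history, whose new-user status and covariates then rest on absence of codes.

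The protocol's position that its pre-index requirement does not act differently by arm is unsupported. It is open to doubt for prior index-drug use, but a differential effect is not shown and its size cannot be derived from the documents. The shifts in the hazard ratio above (up to about 4% for hidden users; 0.92 to 1.09 for fracture history) follow from assumed prevalences, detection rates, hazards and arm differences, and they run in both directions. They show why look-back should be measured; they do not estimate the bias. The point should be corrected before analysis, but it does not by itself invalidate the comparison.

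**What to change.** - Revise the Table 1 row: first observed medical claim and first observed pharmacy claim each at least 12 months before index, plus at least one of each in the 12 months ending the day before index. State what the coverage algorithm requires.
- Derive months of observable look-back, report it by arm before and after matching, and include it in the propensity score.
- Add to section 7.8.10.1 the analysis that Table 1 signals, restricted to longer observed look-back (for example at least 24 months).
- State as a limitation that this reduces misclassification from short look-back but does not recover uncaptured fills or make all five years observable.

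The work is one revised row, one derived variable, one table and one sensitivity analysis, with no extra calendar data. The real cost is patients lost before matching. It cannot be estimated from the documents, because 16,482 abaloparatide and 45,350 teriparatide patients (section 7.1) are counts before the inclusion and exclusion criteria. If the loss threatens the planned 8,000 per arm, apply the stricter look-back as a sensitivity analysis instead and correct the statement in section 7.1.4.

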7.2. Setting

This study will use anonymized patient claims data from PRA (Symphony Health) IDV database. Data are routinely collected in healthcare encounters from all available healthcare sites (inpatient hospital, outpatient hospital, physician's office, etc.) for all types of provided services including specialty, preventive care, and office-based treatments.

The rationale for the study population and the generalizability of the results of these analyses to the general population of postmenopausal women with osteoporosis are discussed in [Section 7.4.2](#).

This is a retrospective observational study evaluating real-world data and, therefore, there are no assigned study visits. The study uses a convenience sample. Patients in the Symphony database who meet the study inclusion/exclusion criteria (Table 1 and Table 2) will be included in the analyses.

7.3. Duration of Subject Participation

Because this is a retrospective claims-based cohort study, subjects included in the analyses will not actively participate in the study and no study visits will be required. The study will use anonymized patient data.

Both effectiveness and cardiovascular safety outcomes will be assessed for patients with 18 months of follow-up data from their index date.

7.4. Study Population

7.4.1. Subject Selection Criteria

Table 1 details the inclusion criteria and Table 2 provides the exclusion criteria for this study.

Table 1 Inclusion Criteria

Criterion	Details	Order of Application	Assessment Window	Code Type	Diagnosis Position	Applied to Study Populations	Varied for Sensitivity	Source for Algorithm
Women	Sex female	Before selection of the index date	Any time	NA	NA	Yes	No	NA
Age: \geq 50 years	\geq 50 years of age	Before selection of the index date	[0, 0]	NA	NA	Yes	No	Proxy for postmenopausal
\geq 1 prescription fill for ABL or TPTD	between May 1, 2017 and June 30, 2019 (identification period)	Will determine the index date	May 1, 2017 and June 30, 2019	NDC	NA	Yes	Yes. Further restriction on various duration of treatment	NA
\geq 1 claim for medical or hospital visit and a pharmacy claim	in the 12 months before the index date	Before selection of the index date	0-12 months pre-index	NDC, ICD, HCPCS	Any	Yes	Yes	PRA proprietary algorithm to determine coverage

ABL = abaloparatide; NA= not applicable; NDC = National Drug Code; post-index = after the index date; pre-index = before the index treatment date; TPTD = teriparatide.

Table 2 Exclusion Criteria

Criterion	Details	Assessment Window	Code Type	Diagnosis Position	Applied to Study Populations	Varied for Sensitivity	Source for Algorithm
Paget's disease	Presence of ≥ 1 claim for Paget's disease	Pre-index	ICD	Any	Yes	No	NA
Malignancy	Presence of ≥ 1 claim except for nonmelanoma skin cancers, carcinoma in-situ of the cervix, ductal carcinoma in-situ of breast	Pre-index	ICD	Any	Yes	No	NA
Indicators of high disease burden and high risk of death	CCI > 10	Pre-index	ICD	Any	Yes	No	NA
With prior index anabolic treatment	Anabolic treatment includes ABL, TPTD and romosozumab	Pre-index	NDC and HCPCS	NA	Yes	No	NA
Switch to a different anabolic treatment after index	Anabolic treatment includes ABL, TPTD and romosozumab	Index-date to 18 months after	NDC and HCPCS	NA	Yes	No	NA

CCI = Charlson Comorbidity Index; ICD = International Classification of Diseases; NA= not applicable; pre-index = before the index treatment date; post-index = after the index date.

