- The primary effectiveness analysis will be an Intention-to-Treat (ITT) analysis.
- The primary safety analysis will be an As-Treated (AT) analysis.

Estimated Sample Size

Between May 2017 and June 2019, a total of 16,482 unique female patients ≥ 50 years of age treated with ABL and 45,350 unique patients ≥ 50 years of age treated with TPTD have been identified in the Symphony database. After applying inclusion/exclusion criteria, the final number of patients will be determined through PS matching. Based on previous studies, it is estimated that approximately 8,000 matched patients will be included in each cohort.

[figure not shown]

[figure not shown]
Sponsor Name: Radius Health, Inc.

Protocol Number: BA058-05-028

Protocol Version and Date: Original, V1.0, dated 09 July 2021

Page 27 of 63

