7.1.1. Rationale for the Current Study Design

Currently, there are no published studies on the effectiveness of ABL in the real-world setting. Furthermore, neither the comparative effectiveness nor comparative safety of ABL versus TPTD have been previously reported. In addition to clinical outcomes evaluated in randomized controlled studies, real-world effectiveness data are important in guiding treatment decisions. An evaluation of real-world effectiveness will provide data on a broader population of patients beyond the patient population included in the ACTIVE trial. Romosozumab is excluded from this study because of its association with an increased risk of cardiovascular events.

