7.8.2. Creation of Analytic Cohorts and Source Data Characteristics

A flow diagram will be provided to reflect the order of operations used to create the analytic cohort from the source database. Temporality of assessment windows will be provided relative to the cohort entry (index date) including additional data to denote exclusion/inclusion criteria and how the final sample was derived.

A table about the source of data (pharmacy claims, medical claims, enhanced hospital claims) will be provided. The table will include calendar time cohort entry (index date) and calendar time range of available data in the pre-index and post-index assessment windows.

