7.8.3. Analysis Populations

Analysis population are all patients meeting the study inclusion/exclusion criteria and selected after propensity matching. The same matched population will used for both effectiveness and safety analysis.

The effectiveness evaluation will be conducted using an ITT analysis, meaning that the first fracture event during the 18 months (+ 30 days follow-up) after the index date will be summarized regardless of when treatment ended. Cardiovascular safety outcomes will be evaluated using an As-Treated (AT) analysis based on only events occurring during the treatment period which is from the index date to the last prescription anabolic drug obtained within the 18 months after the index date, regardless of the anabolic drug possession gap between any 2 prescription fills.

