7.8.6. Effectiveness Analyses

In this study, the primary analyses of effectiveness will be noninferiority analyses for ABL versus TPTD on time to the first incidence of nonvertebral fractures with a margin of 30%. Noninferiority of ABL to TPTD will be concluded if the upper bound of 2-sided 95% CI of HR between ABL versus TPTD is < 1.3.

In a recently published historical control observational study evaluating the real-world effectiveness of osteoporosis therapies using Medicare claim data between 2008 and 2011, the fracture incidence rates for the 12-month pre-treatment period were compared with the 12-month on-treatment period ([Yusuf et al, 2018](#)). For patients treated with TPTD, the incidence rate ratio (IRR [95% CI]) was 0.36 (0.31 to 0.41) for any fracture and 0.34 (0.32 to 0.36) for hip fracture. Based on the EMA and FDA noninferiority margin guidelines ([EMA, 2005](#); [FDA, 2016](#)), if the upper boundary of ABL versus TPTD is $HR < 1.3$, then ABL will preserve approximately 70% of the TPTD benefit, which is higher than the minimum required threshold of 50%.

Comparisons of the time to fracture between the PS-matched ABL and TPTD groups will be based on a Cox proportional hazards model. The hazard ratio (HR) and 95% confidence interval (CI) between the 2 treatment groups will be calculated. The Kaplan-Meier method will be used to estimate event rates. Log rank test will be calculated.

For the fracture outcomes, and the corresponding sensitivity and subgroup analyses, patients will be followed for up to 18 months or until their first fracture event (for the fracture site of interest under evaluation), whichever comes first. All analyses are based on index medication cohort.

The duration, in days, from the date of the first filled prescription for ABL or TPTD to the first incidence of nonvertebral fracture will be derived. If a patient does not experience any nonvertebral fractures during the 18 months of treatment + 30-day follow-up (for a total of 19 months), the patient will be censored at the day of in-hospital death or the 19 months.

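### Table 2 removes women who switch anabolic drug within 18 months after index, even when a fracture or cardiovascular event came first, so membership of the population behind both main analyses depends on post-index information

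*Combined protocol and SAP*

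**What the plan says.** Table 2 (Section 7.4.1) has five exclusion rows. Four are assessed before index. The fifth, "Switch to a different anabolic treatment after index", has the window "Index-date to 18 months after". It covers abaloparatide (ABL), teriparatide (TPTD) and romosozumab, applies to the study populations, and is marked as not varied for sensitivity. No wording limits it to switches that occur before an outcome.

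Section 7.8.5 builds the matched cohorts from women who pass all the criteria. Section 7.8.3 then states "The same matched population will used for both effectiveness and safety analysis". For fractures, Section 7.1 says "The primary effectiveness analysis will be an Intention-to-Treat (ITT) analysis"; Section 7.8.3 explains that the first fracture "will be summarized regardless of when treatment ended"; and Section 7.8.6 adds "All analyses are based on index medication cohort". Fracture follow-up ends at the fracture, at in-hospital death or at the end of the window (Sections 7.6.7.1 and 7.8.6). A switch is not a censoring event.

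The only related rationale is in Section 7.1.1: "Romosozumab is excluded from this study because of its association with an increased risk of cardiovascular events". The limitations in Section 7.1.3 do not mention the switch row.

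**The concern.** A woman who fractures in month 3 and changes anabolic in month 6 meets the exclusion, and her fracture leaves the study with her. A nonfatal MI or stroke followed by a switch is lost in the same way. An in-hospital cardiovascular death cannot be followed by a switch, so the rule can also alter the make-up of the cardiovascular composites.

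Whether a woman counts at time zero therefore depends partly on what happens to her over the next 18 months. If a fracture or cardiovascular event prompts a change of drug, and does so to a different extent in the two arms, the hazard ratio (HR) moves for reasons unrelated to the drugs' effects. At stake are the primary conclusion, which is noninferiority if the upper 95% limit of the HR is below 1.3, and the cardiovascular hazard ratios.

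**Working it through.** **Inputs from the plan.** Fracture rate 3.5% at 18 months and 8,000 matched women per arm (Section 7.8.1.2); margin 1.3 with a two-sided 95% CI (Section 7.8.6), which is 2.5% one-sided. The plan gives no switch rate by arm, outcome or timing.

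**The plan's own figure.** The stated 95% power reproduces as a noninferiority test on the risk difference with margin 0.30 × 3.5% = 1.05 points. SE = sqrt(2 × 0.035 × 0.965 / 8,000) = 0.00291, and Phi(0.0105/0.00291 − 1.96) = 95.1%. This confirms the inputs but says nothing about switching.

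**When the exclusion distorts the HR.** Let a1 and a0 be the shares of ABL women with and without the event who switch, and t1 and t0 the same for TPTD. Removing switchers multiplies the odds of the event in ABL by the retention ratio (1 − a1)/(1 − a0), and in TPTD by (1 − t1)/(1 − t0). Events are uncommon here, so the HR is multiplied by approximately

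b = [(1 − a1)/(1 − a0)] / [(1 − t1)/(1 − t0)].

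The HR is approximately undistorted only when b = 1, that is, when the retention ratios are equal.

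**Tipping point at a true HR of 1.3.** Expected fractures: TPTD 8,000 × 0.035 = 280; ABL 280 × 1.3 = 364. SE of log HR = sqrt(1/364 + 1/280) = 0.0795. The 8,000 is the plan's estimate after exclusions, so these counts are not reduced further. The chance of wrongly concluding noninferiority is Phi(−ln(b)/0.0795 − 1.96).

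- b = 1: 2.5%.
- 5% is reached at b = exp(−(1.960 − 1.645) × 0.0795) = 0.975. Net differential loss: 364 × (1 − b) = about 9 ABL fractures.
- 10% is reached at b = exp(−(1.960 − 1.282) × 0.0795) = 0.9475. Net differential loss: about 19 ABL fractures.

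**Equal association is not enough (all rates assumed).** Take a1 = 10%, a0 = 5%, t1 = 5%, t0 = 2.5%. The switching risk ratio is 2 in both arms, yet b = (0.90/0.95)/(0.95/0.975) = 0.972. With case losses applied, SE = sqrt(1/(364 × 0.90) + 1/(280 × 0.95)) = 0.0825, and the error is Phi(0.0281/0.0825 − 1.96) = 5.3%. If the odds ratio is equalised instead (2.11 in both arms), b = 0.973 and the error is 5.2%. Reversing the arms gives b = 1.028 and 1.1%, which penalises ABL. With low switching (2%, 1%, 1%, 0.5%) the error is 2.9%, close to nominal.

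**Whether anything planned repairs or reveals it.**

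- Section 7.8.5 matches on pre-index variables, after switchers are removed.
- Section 7.8.10 changes the caliper, adds exclusions or changes the cardiovascular endpoint. None of these brings switchers back.
- Section 7.8.9 summarises other osteoporosis treatments only in the matched women.
- Section 7.8.2 plans a flow diagram, but not by arm or by timing relative to the outcome.

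**The case against.** The best defence is the cardiovascular reason for leaving romosozumab out (Section 7.1.1). It explains part of the row and could justify ending follow-up at a romosozumab fill. It does not require deleting events that came before the fill, and it does not cover switches between ABL and TPTD.

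A reader might infer that the plan breaches its own ITT definition. The documents do not go that far. Section 7.8.3 counts fractures whenever treatment ended, among women who pass the criteria, and the index-cohort rule in Section 7.8.6 assigns analysed women to arms. Neither says whether switchers enter the cohort. The objection is to the design choice: an analysis from which future switchers have been removed loses the protection that the ITT label suggests.

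A reader might also infer that the rule favours ABL. Nothing in the documents supports a direction; the same arithmetic run with the arms reversed works against ABL. The illustrative rates have no documentary basis. Only the tipping point rests on the plan's inputs, and it does not show that a net loss of 9 fractures is likely.

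The exclusion is not wholly hidden. The flow diagram is to show data "including additional data to denote exclusion/inclusion criteria and how the final sample was derived", so a total number of switchers may appear. A total would not show whether the two arms lost events differently.

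**Conclusion.** The concern holds as a design weakness that should be fixed. The text establishes that eligibility uses post-index information, that outcome events followed by a switch are deleted from both the fracture and the cardiovascular analyses, and that no planned analysis undoes this.

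The consequence is not established. With equal retention ratios the HR is essentially unchanged and only events are lost; with rare switching the distortion is small in either direction. The margin for error is narrow all the same: at a true HR of 1.3, a net differential loss of about 9 of 364 ABL fractures doubles the false noninferiority rate to 5%, and about 19 takes it to 10%. These figures assume the plan's 3.5% and 8,000 per arm and an approximately normal log HR. The planned outputs would not show which case applies.

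**What to change.** 1. Remove the post-index switch row from Table 2, define eligibility from pre-index and index data only, and rerun the matching.
2. Keep switchers in their index cohort for the primary ITT fracture analysis, and state that this analysis decides noninferiority.
3. Add a sensitivity analysis that censors fracture follow-up at the switch date. Report the present exclude-switchers version as a sensitivity analysis only.
4. In the as-treated safety analysis, keep switchers, end their follow-up at the switch date, and state how this fits the 30-day window in Section 7.8.7. Time after a switch to romosozumab then stays out without deleting earlier events.
5. In the Section 7.8.2 flow diagram, show switch counts by arm, destination drug and timing relative to the first fracture or cardiovascular event.

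The cost is protocol wording, a rerun of selection and matching, and one added fracture analysis. No new data are needed unless the June 2021 extraction (Table 3) had already applied this row, in which case the switchers must be extracted again.

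There are two statistical downsides. Retained cross-over between ABL and TPTD dilutes the HR toward 1, which eases noninferiority. If 5% of person-time in each arm crosses over (an assumption), 1.30 becomes (0.95 × 1.3 + 0.05)/(0.95 + 0.05 × 1.3) = 1.27; the true amount depends on cross-over time that the documents do not give. Censoring at the switch avoids that dilution but may itself be informative. This is why the censored result should be reported beside the ITT result.
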